4. STUDY ASSESSMENTS

Study Assessments	Pre-Screening	Baseline (T1)	Post-Intervention (T2)	8-Month Follow-Up (T3)
Screener Questionnaire (SCR)	X			
Eligibility Form (ELG)		X		
Baseline Questionnaire (BSL)		X		
Biospecimen Collection Form (BIC)		X		X
Biospecimen Lab Results Form (BLR)		X		X
Workshop Tracking (WTI)			X	
Workshop Evaluation (EVL)			X	
Exit Visit Questionnaire (EXQ)				X

4.1. Primary Outcomes

4.1.1. Information Systems Success Model Score (T2)

The Information Systems Success Model (ISSM) will be used to assess for intervention acceptability and satisfaction. The 21-item scale measures four sub-domains: information quality, handbook quality, perceived usefulness, and overall satisfaction. Every item is scored on a 1 to 5 scale, with 1 being “Strongly Disagree” and 5 being “Strongly Agree”. Responses are averaged within each sub-domain to produce four sub-domain scores. The four sub-domain scores are then averaged to produce an overall ISSM score (range: 1 to 5; higher scores indicate higher acceptability/satisfaction). This scale has been adapted from Horvath et al.¹

4.1.2. Workshop Completion (T2)

Workshop completion will be used to assess for intervention feasibility. The outcome of intervention completion will be defined as having attended at least two of the four workshop sessions and will be measured by tracking participant attendance. Workshop completion may also be defined as the number of workshop sessions attended for use in exploratory analyses.

4.1.3. Change in Job-Seeking Self-Efficacy Scale Score (T1 to T3)

Job seeking self-efficacy is defined as one's perceived ability and confidence to perform job search and application activities. The 12-item Job Seeking Self-Efficacy (JSS) scale by Barlow et al² uses response values on a 1 to 10 score, with 1 being "Not At All Confident" and 10 being "Very Confident". Responses are averaged to yield a total score, with higher scores indicating higher self-efficacy. Change in JSS will be calculated by subtracting the JSS score at baseline (T1) from the JSS score at the 8-month follow-up (T3) (range: -9 to +9; negative change indicates decreased self-efficacy, while positive change indicates increased self-efficacy).

4.1.4. Change in Protean Career Attitudes Scale Score (T1 to T3)

Protean career attitudes (PCAs) are defined as having self-direction in the pursuit of success in one's work. PCAs have previously been found to be associated with positive career satisfaction and self-perceived success.³ The validated 7-item scale by Porter et al⁴ measures two sub-domains: self-directed attitudes and values-driven attitudes. Every item is scored on a 1 to 5 scale, with 1 being "Strongly Disagree" and 5 being "Strongly Agree". Responses are averaged within each sub-domain to produce two sub-domain scores, which are then averaged as well to produce an overall PCA score. Change in PCA score will be calculated by subtracting the score at baseline (T1) from the score at the 8-month follow-up (T3) (range: -4 to +4; negative change indicates decreased PCAs, while positive change indicates increased PCAs).

4.2. Secondary Outcomes

4.2.1. Change in Self-Reported Hours Worked Per Week (T1 to T3)

Hours worked per week will be self-reported at baseline and at the 8-month follow-up visit as any value between 0 and 99. Change in hours worked per week will be calculated by subtracting the baseline (T1) value from the 8-month follow-up (T3) value. Negative change indicates fewer hours worked per week, while positive change indicates more hours work per week.

4.2.2. Change in Self-Reported Sexual Risk Behaviors (T1 to T3)

Sexual risk behaviors will be measured using six yes or no (1 or 0) items assessing for engagement in the following behaviors during the 6 months prior to baseline (T1) and 8-month follow-up (T3) assessments:

1. condomless anal intercourse (CAI) with male partner of unknown HIV status
2. anal intercourse with ≥ 3 males
3. sex with male partner with a Sexually Transmitted Infection (STI)
4. CAI with HIV+ male partner
5. anal intercourse with condom failure
6. transactional sex work involvement

Responses will be averaged at each assessment. Change in sexual risk behaviors will be calculated by subtracting the average at baseline from the average at the 8-month follow-up (range: -1 to +1; negative change indicates fewer sexual risk behaviors, while positive change indicates more sexual risk behaviors).

4.2.3. Change in Chlamydia Test Result (T1 to T3)

Chlamydia infections will be assessed at baseline and 8-month follow up using oral, anal, and urine samples. Each of the three tests yields a positive (1) or negative (0) result. Change in test result will be calculated by subtracting the baseline result from the 8-month follow-up result. Oral, anal, and urine tests will be treated as separate outcomes.

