### 3.4 Biological Specimens

Project staff members who have completed mandatory training will conduct HIV/STI testing. Study participants will be screened for drug use and STIs such as chlamydia, gonorrhea, syphilis, and HIV

infection at the baseline and follow-up visits. Clinical specimens may include 15-20 mL first-catch urine, anal swab (GC,CT), oral/laryngeal swab, and finger stick. Participants with reactive STI or HIV tests will be referred to affiliated clinics at each site for evaluation and treatment. All participant referral clinics will be comprehensive and follow the Ryan White HIV/AIDS Programming instruction as developed by the HRSA HIV/AIDS Bureau. Senior Investigators are practicing physicians at study referral sites with experience in YMSM and YTW health, and will provide any subsequent mental health, medical case management, and psychosocial support service referrals as needed for participants. Following the protocols of our previous studies involving HIV testing, HIV-positive participants at follow-up will not receive HIV testing if they produce documentation of a previous diagnosis (e.g., medications, lab report). In addition, phase 3 participants with a known HIV positive status at the time of consent will not receive HIV testing at baseline or follow-up.

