5.5. Analysis of Secondary Outcomes

Secondary outcomes for analyses include change in self-reported hours worked per week, change in self-reported sexual risk behavior, change in chlamydia test results, change in gonorrhea test results, and reactive HIV test result. Details about these outcomes are described in Section 4.2.

Univariate analyses will be performed as described in Section 5.1. Multivariable analyses will adjust for sociodemographic characteristics, workshop attendance, baseline employment status, and study completeness. Analytical models will include linear regression or generalized linear models for continuous outcomes and logistic regression for binary and categorical outcomes.

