2.3.3. Change in Chlamydia Result from Baseline to Month 8 Follow-Up (T1T3)

2.3.3.1. Change in Chlamydia Result based on Oral Samples at T1T3

Description: Change in Chlamydia oral sample result of a participant from Baseline to Month 8 follow-up (T1 to T3)

Variable: CH_ORAL_T1T3_1

Label: Change in Chlamydia Oral Sample Result from T1 to T3 (T3-T1)

Type: Numeric; Format: 1=Negative to Positive, 0=No Change in Gonorrhea Anal Result, -1=Positive to Negative

Algorithm: CH_ORAL_T1T3_1 = CH_ORAL_T3_1 – CH_ORAL_T1_1

If measurement at either time point is missing, then CH_ORAL_T1T3_1 = missing.

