2.4.3. Change in Gonorrhea Result from Baseline to Month 8 Follow-Up (T1T3)

2.4.3.1. Change in Gonorrhea Result based on Oral Samples at T1T3

Description: Change in Gonorrhea oral sample result of a participant from Baseline to Month 8 follow-up (T1 to T3)

Variable: GN_ORAL_T1T3_1

Label: Change in Gonorrhea Oral Sample Result from T1 to T3 (T3-T1)

Type: Numeric; Format: 1=Negative to Positive, 0=No Change in Gonorrhea Oral Result, -1=Positive to Negative

Algorithm: $GN_ORAL_T1T3_1 = GN_ORAL_T3_1 - GN_ORAL_T1_1$

If measurement at either time point is missing, then $GN_ORAL_T1T3_1 = \text{missing}$.

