4.2.3. Change in Chlamydia Test Result (T1 to T3)

Chlamydia infections will be assessed at baseline and 3-month follow up using oral, anal, and urine samples. Each of the three tests yields a positive (1) or negative (0) result. Change in test result will be calculated by subtracting the baseline result from the 3-month follow-up result. Oral, anal, and urine tests will be treated as separate outcomes.

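### The subtracted chlamydia and gonorrhea outcomes merge participants positive at both visits with those never positive, and modelling them without the baseline result can create associations through the coding alone

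*SAP*

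**What the plan says.** Section 4.2.3 of the Phase 2 SAP scores chlamydia at three sites (oral, anal, urine), each a separate outcome: "Each of the three tests yields a positive (1) or negative (0) result". It then takes the difference: "Change in test result will be calculated by subtracting the baseline result from the 8-month follow-up result". Section 4.2.4 applies the same rule to gonorrhea. The Phase 3 SAP repeats both sections with its shorter follow-up: "Change in test result will be calculated by subtracting the baseline result from the 3-month follow-up result".

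The appendices allow three values. For oral gonorrhea (Phase 2 Appendix 2.4.3.1) they are "1=Negative to Positive, 0=No Change in Gonorrhea Oral Result, -1=Positive to Negative". The chlamydia variables use the same three codes, although the zero level carries a gonorrhea label (Phase 2 Appendix 2.3.3.1: "1=Negative to Positive, 0=No Change in Gonorrhea Anal Result, -1=Positive to Negative"). That is a labelling slip and does not alter the values.

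Section 5.5 of both SAPs lists as secondary outcomes "change in chlamydia test results, change in gonorrhea test results, and reactive HIV test result". The adjusted models contain demographics, workshops attended, employment at baseline and completeness of participation. The baseline STI result is not among them. The model type is "logistic regression for binary and categorical outcomes", with linear or generalized linear models for continuous outcomes. Nothing says which applies to a variable typed as numeric that takes -1, 0 or +1. Section 5.4 makes its adjusted models conditional on the data being sufficient; Section 5.5 has no such condition.

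The univariate test in Section 5.1 is McNemar's, and outcomes are also to be described at each visit. For HIV, Section 4.2.5 uses the follow-up result directly, without subtraction.

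**The concern.** Both SAPs hypothesise fewer STIs. A participant positive at follow-up is infected at follow-up whatever the baseline result, yet the change variable gives the both-positive participant the same code as one never found infected. Protocol 3.4 says "Participants with reactive STI or HIV tests will be referred to affiliated clinics at each site for evaluation and treatment", so the both-positive group is one that a reader of the results would want to see.

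The second problem is structural. The score is tied to baseline status, because -1 is open only to baseline positives and +1 only to baseline negatives. A covariate that goes with baseline infection can therefore be associated with the score because of where people started, and the models hold nothing that accounts for the starting point. Such an association could be reported as a finding about who benefits.

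**Working it through.** The documents give no STI rate, event count or power figure, so there is no stated figure to reproduce. All rates below are assumptions. The figure of 50 pairs is the Phase 2 completer target (SAP 2.3), taking every completer to have both specimens at the site in question.

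**1. The coding.** Difference = T3 - T1.

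| T1 | T3 | Score |
|---|---|---|
| 0 | 0 | 0 |
| 0 | 1 | +1 |
| 1 | 0 | -1 |
| 1 | 1 | 0 |

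This holds for 2 infections x 3 sites x 2 phases = 12 variables.

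**2. How many people are merged.** Let p = proportion positive at T1, q = proportion of those positive at T3, and s = proportion of T1-negatives positive at T3.

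- Both-positive count = 50pq. Share of T3 positives coded 0 = pq / [pq + (1-p)s].
- Middle case, p = 0.10, q = 0.20, s = 0.05: 50 x 0.02 = 1.0 person; the other T3 positives number 50 x 0.90 x 0.05 = 2.25; share = 1.0/3.25 = 31%.
- Over p = 5-20%, q = 10-40%, s = 5-10%, the count runs from 50 x 0.05 x 0.10 = 0.25 to 50 x 0.20 x 0.40 = 4. The share runs from 0.005/(0.005 + 0.095) = 5% to 0.08/(0.08 + 0.04) = 67%.
- All T3 positives at a site number about 2.6 (0.25 + 2.375) to 8 (4 + 4).

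**3. What a model of the score shows.** Two groups are compared, with T3 taken as independent of T1 within each group and the three levels treated as unordered categories. For baseline rate a and follow-up rate b: P(-1) = a(1-b), P(+1) = (1-a)b, P(0) = the remainder, and mean change = b - a.

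| Scenario (T1 to T3) | P(-1), P(0), P(+1): low-baseline group | Same: high-baseline group | OR, -1 v 0 | OR, +1 v 0 | Difference in mean change |
|---|---|---|---|---|---|
| Both stable: 5% to 5%, 25% to 25% | 0.0475, 0.905, 0.0475 | 0.1875, 0.625, 0.1875 | 5.7 | 5.7 | 0 |
| Same T3 rate: 5% to 10%, 25% to 10% | 0.045, 0.860, 0.095 | 0.225, 0.700, 0.075 | 6.1 | 0.97 | -0.20 |
| High group worsens: 5% to 5%, 25% to 37.5% | 0.0475, 0.905, 0.0475 | 0.156, 0.5625, 0.281 | 5.3 | 9.5 | +0.125 |

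First row: (0.1875/0.625) / (0.0475/0.905) = 0.300/0.0525 = 5.7. The odds of -1 are raised in every row. The linear comparison shows apparent improvement only in the second.

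**4. Chance of a significant result in a linear model.** Each scenario was simulated 2,000 times with group as the only covariate, at the SAP's 0.1 level taken as two-sided (nominal 5% in the direction of improvement). The T3 rate was 10% in both groups.

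| Baseline rates | n | Change score on group | T3 on group + T1 |
|---|---|---|---|
| 5% v 15% | 50 | 23% | 6% |
| 5% v 25% | 50 | 45% | 5% |
| 5% v 15% | 40 | 19% | 4% |
| 5% v 25% | 40 | 38% | 4% |

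When each group kept its own rate, the change-score model declared improvement in 5% to 6% of runs, which is about nominal.

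**The case against.** Five points can be made for the plan as written.

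- **The main test is sound.** McNemar's test uses only discordant pairs, so both-positive participants carry no weight there by design. The mean of T3 minus T1 is exactly the change in prevalence, for which a both-positive pair is properly neutral. This stands.
- **Nothing is lost from the data.** The T1 and T3 results are kept as separate variables, and outcomes are described at each visit. Among paired specimens, the both-positive count equals T3 positives minus those coded +1. This stands, except that specimens are optional (Protocol 8.3), so visit totals need not be restricted to pairs, and no four-cell table is planned.
- **Change is a legitimate target in a pre/post study.** Where a group really falls from 25% to 10%, its change does differ from that of a group going from 5% to 10%, and calling this spurious partly reflects a preference for comparing follow-up status given baseline. This stands for the linear model. It does not explain the categorical model, where the odds of -1 rise 5.7-fold with no change in either group.
- **Repeat infection is not established.** A reader might infer that a both-positive pair is a new infection after treatment. The protocol provides for referral, which does not show that treatment was received, so persistence cannot be excluded.
- **The counts are tiny.** The 31% in the middle case is one person. With roughly 3 to 8 follow-up positives per site, any adjusted model is fragile, including the one proposed below. This stands and limits the fix.

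**Conclusion.** The coding defect is exact and present in all 12 STI change variables. Omitting the baseline result from the Section 5.5 models means that covariate associations can arise from the coding. Under the assumed rates, the odds ratio for -1 versus 0 was 5.3 to 6.1 when baseline prevalence was 5% against 25%, whether the second group fell, stayed level or worsened.

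A reader might go further and infer that the adjusted models will show false improvement in groups with more infection at baseline. The documents do not support that. They do not say how the three-level variable is modelled. In a linear model the effect appears only if the high-baseline group falls back toward the other; it vanishes if both stay level and reverses if that group worsens. In the categorical model, the stable and worsening cases raise the odds of +1 as well as -1.

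The consequence is limited to exploratory secondary outcomes in an unpowered pilot, and to about 0.25 to 4 both-positive people among 50 pairs. All of these sizes rest on assumed rates, and the odds ratios also on independence of the two visits within groups. The correction is worth making because it is cheap, but the paired test does not depend on it.

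**What to change.** In both SAPs:

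1. Keep McNemar's test on the paired results.
2. In 4.2.3, 4.2.4 and the appendix, report the four T1-by-T3 cells (negative-negative, negative-positive, positive-negative, positive-positive) for each infection and site, in place of -1/0/+1 frequencies. Correct the gonorrhea label on the chlamydia variables at the same time.
3. In 5.5, replace the subtracted variable as the modelled outcome with the T3 result (0/1), with the same-site T1 result as a covariate. This is close to what the plan already does for HIV.
4. State that these models are fitted only as far as event counts allow, with few covariates or a penalised or exact method, and that the STI results are otherwise descriptive only.

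The cost is SAP wording and a recode of variables already derived, with no new data and no effect on enrolment. The model then answers who is infected at follow-up given baseline status, rather than who changed, and the text should say so. The downside is that the adjusted STI models may prove too sparse to report. The four-cell tables would still show the group that the present coding merges.

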### 8.3 Compensation

**Focus Groups:** Participants will receive \$40 each for focus group participation.

**Key Informant Interviews:** LGBTQ-friendly employers will be offered a \$10 gift card for key informant interview participation. All other participants will receive \$40 for key informant interview participation.

**CAB:** \$30 per meeting.

**Intervention Pre-Test:** Participants will receive \$30 for completing visit surveys at T1 and T2, \$40 for providing optional biologic specimens at T1, and \$20 per workshop session attended, for a possible total of \$180.

**Intervention Pilot:** Participants will receive \$30 for completing visit surveys at each time point, \$40 for providing optional biologic specimens at T1 and T3, \$40 per workshop session attended, for a possible total of \$330.

**Intervention Community Pilot:** Participants will receive \$30 for completing visit surveys at each time point, \$40 for providing optional biologic specimens at T1 and T3, and \$30 per workshop session attended, for a possible total of \$290.

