1.1. Objectives and Research Hypotheses

The primary objective of Phase 2 is to pilot-test the intervention among up to 70 at-risk YMSM and YTW of color in order to evaluate feasibility and acceptability. Investigators hypothesize the intervention will increase job self-efficacy and readiness, as well as decrease HIV risk behaviors and STI and HIV infections.

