2.3. Sample Size Information

This study aims to enroll up to 70 participants with at least 50 of these participants completing the study (~70% retention rate). Given the exploratory nature of this study and limited access to this population, a power calculation was not performed. A repeated measures design was chosen to reduce the variability in the estimate of the treatment effect, at the expense of having a comparison group. In addition, practice or fatigue effects from repetition may affect certain outcomes (e.g. protean career attitudes scale and subscales). This trade-off was appropriate given the exploratory nature of a pilot study and the limited access to the study population.

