4.2.4. Change in Gonorrhea Test Result (T1 to T3)

Gonorrhea infections will be assessed at baseline and 8-month follow up using oral, anal, and urine samples. Each of the three tests yields a positive (1) or negative (0) result. Change in test result will be calculated by subtracting the baseline result from the 8-month follow-up result. Oral, anal, and urine tests will be treated as separate outcomes.

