5. STATISTICAL ANALYSIS

5.1. General Considerations

The analytic plan is designed to determine preliminary efficacy of the intervention by comparing pre/post assessments of employment and sexual risk behaviors. Descriptive statistics will be used to analyze the proportions and central tendencies for participant sociodemographic covariates collected in the surveys. We will first generate frequencies, means, and other measures of central tendency as appropriate to describe our sample and outcomes at each of the three time points (baseline, post-intervention, and 8-month follow-up).

Changes in primary and secondary outcomes between baseline and 8-month follow-up will be assessed using paired t-tests for continuous variables and McNemar's test for matched categorical variables. We will use standard diagnostic tools to assess the appropriateness of the normality assumption (e.g., QQ-plots) and, if approximate normality of the residuals is not tenable, a non-parametric test for continuous paired data, i.e. Wilcoxon sign rank test will be used. All hypothesis testing will be done at an alpha-level of 0.1, given the exploratory nature of the study.

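### Chlamydia and gonorrhea are analysed only site by site, so no pre-specified result says whether fewer participants were infected

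*SAP*

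**What the plan says.** Section 1.1 of the Phase 2 SAP states: "Investigators hypothesize the intervention will increase job self-efficacy and readiness, as well as decrease HIV risk behaviors and STI and HIV infections". The Phase 3 SAP carries the same hypothesis.

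The STI outcomes are defined by specimen. For gonorrhea in Phase 2, section 4.2.4 says "Gonorrhea infections will be assessed at baseline and 8-month follow up using oral, anal, and urine samples", and section 4.2.3 is parallel for chlamydia. Both sections add "Oral, anal, and urine tests will be treated as separate outcomes". Phase 3 repeats this with a 3-month follow-up. Appendix sections 2.3.3 and 2.4.3 of each SAP derive six change variables (T3 minus T1), each set to missing if the result at either visit is missing.

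Section 5.5 lists "change in chlamydia test results, change in gonorrhea test results, and reactive HIV test result". Neither that list, section 4.2 nor the appendix contains an any-site or any-STI variable.

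Section 5.1 assigns "McNemar's test for matched categorical variables" and adds: "All hypothesis testing will be done at an alpha-level of 0.1, given the exploratory nature of the study". It does not say whether McNemar is exact or asymptotic, does not state sidedness, and has no multiplicity rule.

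Phase 2 aims for up to 70 enrolled and at least 50 completing. Phase 3 aims for up to 40 and gives no completer target. Both SAPs say that power was not calculated. Protocol 8.3 pays participants for "providing optional biologic specimens at T1 and T3", so specimens are voluntary. Protocol 3.4 refers participants with reactive tests for evaluation and treatment.

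**The concern.** The hypothesis concerns whether infections decline among participants, but the analysis answers six narrower questions, such as whether pharyngeal chlamydia positivity changed. The six answers can point in different directions, and the plan has no rule for reading them together. Someone infected at both visits, at different sites, appears as a gain in one table and a loss in another.

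Splitting by site also thins the data. McNemar's test uses only discordant pairs, and each site table is limited to participants who gave that specimen at both visits. At stake is whether the trial can report one interpretable STI estimate, or only six imprecise ones from which a chance result could be singled out.

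**Working it through.** **1. The plan's own figure.** 50/70 = 71.4%, and 70 × 0.70 = 49, so the stated retention of about 70% is consistent with 50 completers. There is no power figure to reproduce.

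**2. The site-switch case (no prevalence needed).** Take a participant oral-positive and anal-negative at T1, then oral-negative and anal-positive at T3. Oral change is 0 − 1 = −1, anal change is 1 − 0 = +1, and any-site change is 1 − 1 = 0.

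**3. Fewest discordant pairs for p ≤ 0.10, all in one direction (two-sided assumed).** Exact: p = 2 × 0.5^m, so m = 4 gives 0.125 and m = 5 gives 0.0625; five are needed. Uncorrected asymptotic: z = √m, so m = 3 gives p = 0.083; three are enough.

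**4. Power and false positives per site test.** From the documents: n = 50 pairs (Phase 2 completer target) and alpha 0.10. Assumed: site positivity p1 of 4-12%, halved at T3 (p3 = p1/2), with T1 and T3 independent within a participant.

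- P(positive to negative) = p1(1 − p3) and P(negative to positive) = p3(1 − p1). At 8%: 0.08 × 0.96 = 0.0768 and 0.04 × 0.92 = 0.0368, so 50 × 0.1136 = 5.7 discordant pairs are expected.
- Power is by full enumeration of the discordant counts, counting rejections in the direction of a fall.
- Size is the same enumeration with no change, p1(1 − p1) each way, counting rejections in either direction.
- The six-test figure is 1 − (1 − size)^6.

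| Site positivity at T1 | Expected discordant pairs | Power, exact | Power, asymptotic | Size, exact | Any of six, exact | Any of six, asymptotic |
|---|---|---|---|---|---|---|
| 4% | 2.9 | 0.020 | 0.128 | 0.0156 | 0.090 | 0.468 |
| 8% | 5.7 | 0.088 | 0.200 | 0.0375 | 0.205 | 0.469 |
| 12% | 8.3 | 0.156 | 0.275 | 0.0487 | 0.259 | 0.486 |

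The nominal figure is 1 − 0.9^6 = 0.469. The asymptotic test roughly attains it, while the exact test is well below it because it is conservative with few discordant pairs. Correlation between sites in the same person would change all the six-test figures.

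**5. Sensitivity to the assumptions (exact test).**
- Halving, 50 pairs: power 3.5% at 5% site positivity (3.6 discordant pairs expected), 21% at 15% (10.1 pairs) and 30% at 20% (13.0 pairs).
- Halving, all 70 enrolled giving pairs: 7% at 5% and 19% at 10%.
- Halving, Phase 3 with all 40 giving pairs: 1.9% at 5%, 8.8% at 10% and 16% at 15%.
- Every baseline positive clears and no new infections occur, 50 pairs: 10% at 5%, 57% at 10% and 89% at 15%.

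**6. What an any-site outcome gains.** Any-site positivity lies between the largest site rate (complete overlap) and the sum of the three (no overlap). With equal rates of 4% and 8%, the ceilings are 12% and 24%. With 50 pairs and a halving, exact power at those ceilings is 16% and 37%. With complete overlap it stays at the single-site 2.0% and 8.8%. By the normal-approximation McNemar formula, 80% power to detect a halving needs about 221 pairs at 15% any-site positivity, 159 at 20% and 97 at 30%. The number of tests falls from six to two, and the nominal chance of any false positive to 1 − 0.9^2 = 0.19.

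**The case against.** The case for leaving the plan alone has substance. These are secondary outcomes in a pilot whose SAPs set feasibility and acceptability as the primary objective and disclaim power, so no stated error or power target is missed. Low power comes mainly from the sample size, and step 6 shows that pooling sites does not cure it. Site-level reporting is a legitimate choice: because baseline positives are referred for treatment, a person who switches site may have cleared one infection and acquired another. The site variables record both events, whereas an any-site variable records no change. All site results are retained, so a person-level summary could be derived later without new data.

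Most of this stands, but it does not supply the missing result. An exploratory study still needs an estimate of the quantity in its own hypothesis, and a summary chosen after the six results are known is weaker than one named beforehand. Even if the hypothesis is read as counting infections rather than infected people, the plan defines no such count.

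Three stronger readings are tempting and are not supported:

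- A reader might infer that the site tests could not show a fall at all. Prevalence is not given, and near-complete clearance at 15% site positivity would be detected with 89% power.
- A reader might pair 2-16% power with a 47% chance of a false positive. Those belong to different versions of the test, and the SAPs do not say which applies.
- A reader might expect an any-site outcome to bring adequate power. At 4% per site, any-site positivity cannot exceed 12%, where power is about 16%.

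**Conclusion.** The concern holds in a limited form. On the text alone, with no assumption about prevalence, both SAPs lack a pre-specified result for whether fewer participants had chlamydia or gonorrhea, and the site-level scoring can split one infected person into an improvement and a worsening.

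The size of the statistical problem is conditional. It rests on assumed site positivity of 4-12%, a halving, independence of visits within a person, 50 usable pairs and, for the six-test figures, independence between tests. Fewer pairs, through declined specimens or in Phase 3, would lower power. Higher prevalence or a larger effect would raise it. The false-positive range depends more on the unstated version of McNemar than on prevalence.

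This is a worthwhile, cheap improvement to a secondary analysis. It does not threaten the trial's primary objective.

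**What to change.** In sections 4.2.3 and 4.2.4 of both SAPs, with matching entries in section 5.5 and the appendix:

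- Add one person-level outcome per organism as the main STI summary: positive at any site, using only sites sampled at both T1 and T3.
- Test each with exact McNemar, and report the paired change in proportion with a confidence interval.
- Report oral, anal and urine changes descriptively, without p-values.
- State how many participants contribute one, two or three sites.
- Note that a fall may reflect referral and treatment of infections found at baseline rather than the intervention.

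The cost is one derived variable per organism and some SAP wording, with no new visits or specimens. There are three downsides. Any-site positivity covers one to three sites depending on the participant. Someone who clears one site and acquires another counts as unchanged, although the descriptive site results still show it. Power remains low, so the confidence interval should carry the interpretation.
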